6.3 Definition of Analyzed Study Population

All patients who underwent a [⁶⁸Ga]DOTATATE-PET/MRI or PET/CT scan will be included in the analysis.

6.4 Statistical Analysis Plan

This study will largely be exploratory and descriptive. For all clinical and histological evaluations as well as imaging parameters, we will generate summary tabulations of the number of observations, mean, standard deviation, median, minimum, and maximum for continuous variables, and the frequency and percentage for categorical variables. Analyses will be primarily descriptive and graphical in nature. The count, and percentage of patients with HCCs showing activity in their HCC greater than liver and/or spleen will be estimated using Clopper-Pearson (exact) method along with two-sided 95% CI. The estimation will be provided for all 30 patients first, and then by treatment-naïve or not.

Concordance between [⁶⁸Ga]DOTATATE PET results and liver MRI results for patients with SSTR-positive HCC and positive [⁶⁸Ga]DOTATATE PET, intrahepatic and extrahepatic disease will be assessed on MRI/CT alone first, with confidence in interpretation rated on a 1-5 scale (1 = negative, 5 definite). Following this, fused PET/CT or PET/MRI images will be assessed and rated on the same 1-5 scale. Scale 3-4

is defined as positive. The agreement (concordance) between nominal (e.g. scale 1-5) or binary outcome (positive or negative) of [⁶⁸Ga]DOTATATE PET results and liver MRI results will be assessed using Cohen's kappa coefficients with one-side 95% confidence intervals. Based on values of Cohen's kappa, the agreement will be considered as poor (>0.2), fair (0.21-0.40), moderate (0.41-0.60), good (0.61-0.80), and very good (0.81-1.0) ([Dtsch Arztbl Int. Concordance Analysis. 2011 Jul; 108\(30\): 515-521. PMID: 21904584](#)). Bland-Altman diagrams will be used to evaluate agreement for other continuous imaging variables between these two methods. All statistical analysis will be carried on SAS v9.4.

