1.0 Introduction and Study Rationale

1.1 Overview

There is great need for new therapeutic options for patients with hepatocellular carcinoma (HCC). This study will assess the feasibility of a novel theranostic approach to hepatocellular carcinoma (HCC) using [⁶⁸Ga]DOTATATE, a recently FDA-approved positron emission tomography (PET) ligand for imaging somatostatin receptor (SSTR) positive tumors. This PET tracer is in routine clinical use for neuroendocrine tumors (NET) but to our knowledge has not been systematically applied to HCC. The objective of this study is to measure the frequency of SSTR positivity in hepatocellular carcinoma using [⁶⁸Ga]DOTATATE-PET. We hypothesize that [⁶⁸Ga]DOTATATE-PET will be positive in at least 20% of patients with HCC. If this current study shows a substantial fraction HCCs have moderate to high SSTR levels based on PET imaging, this result would justify future studies evaluating targeted radionuclide therapy (TRT) with the therapeutic SSTR ligand [¹⁷⁷Lu]DOTATATE which was recently FDA approved for treating SSTR-positive NETs arising from the gastrointestinal tract.

Study objective: Determine the frequency of somatostatin receptor positivity in hepatocellular carcinoma using [⁶⁸Ga]DOTATATE-PET

Hypothesis: [⁶⁸Ga]DOTATATE PET will be positive in at least 20% of patients with hepatocellular carcinoma (HCC).

In this study, patients with treatment-naïve HCC (n=15) and patients with previously treated HCC being referred for systemic chemotherapy and/or best supportive care (n=15) will be enrolled. Patients will undergo a single whole body [⁶⁸Ga]DOTATATE-PET/MRI to assess SSTR positivity of their HCCs. The percentage of patients with HCCs showing activity in their HCC greater than liver and/or spleen will be calculated.

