4.6.4 PET/CT and PET/MRI Imaging Interpretation and Storage

Images from the PET/CT and PET/MRI will be anonymized and subsequently stored and reviewed using a commercially available software package (MIM Encore, Cleveland, OH). The PET and whole body MRI studies will not be available in the UAB PACS system. This is in an effort to blind the treating physicians from making clinical decisions on an experimental imaging technique. The liver MRI images will be sent to clinical PACS and the medical record as part

of standard-of-care imaging and can be used in the clinical-decision making process. No formal interpretation will be generated for the [⁶⁸Ga]DOTATATE-PET or whole body MRI portion of the study.

PET/CT and PET/MRI images will be interpreted by board certified physicians specialized in molecular imaging and abdominal imaging. Images will initially be interpreted as positive or negative for SSTR-positive HCC. HCC lesions will be considered SSTR positive for the purposes of this study if they have higher [⁶⁸Ga]DOTATATE activity than adjacent liver not involved by HCC. The amount of [⁶⁸Ga]DOTATATE binding for intrahepatic HCCs will be further characterized based on visual analysis as less than skeletal muscle (no binding), higher than skeletal muscle but less than or equal to adjacent liver (low binding), higher than adjacent liver but less than spleen (moderate binding) or equal to or greater than spleen (high binding). For patients with SSTR-positive HCC and positive [⁶⁸Ga]DOTATATE PET, intrahepatic and extrahepatic disease will be assessed on MRI/CT alone first, with confidence in interpretation rated on a 1-5 scale (1 = negative, 5 definite). Following this, fused PET/CT or PET/MRI images will be assessed and rated on the same 1-5 scale.

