5.0 Study Parameters

5.1 Primary Endpoint

- Percentage of patients with moderate to high binding of [⁶⁸Ga]DOTATATE on PET examination
- Concordance between [⁶⁸Ga]DOTATATE PET results and liver MRI results

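### The rules behind the primary percentage are not mutually consistent: low and high binding overlap when spleen uptake is at or below liver, and the and/or wording in 1.1 and 6.4 is left open

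*Combined protocol and SAP*

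**What the plan says.** All references are to the combined protocol and SAP.

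- Section 5.1 gives the first primary endpoint as "Percentage of patients with moderate to high binding of" the tracer. Section 6.2 names the same quantity as what the 30 patients are enrolled to estimate.
- Section 4.6.4 first reads images as positive or negative. A lesion is SSTR-positive if it has higher "activity than adjacent liver not involved by HCC".
- Section 4.6.4 then grades intrahepatic lesions visually. Below skeletal muscle is no binding. Low is "higher than skeletal muscle but less than or equal to adjacent liver (low binding". The two grades above that are "higher than adjacent liver but less than spleen (moderate binding) or equal to or greater than spleen (high binding".
- Section 1.1 says the percentage of patients "showing activity in their HCC greater than liver and/or spleen will be calculated". Section 6.4 uses the same phrase for the analysis itself: activity "greater than liver and/or spleen will be estimated using Clopper-Pearson (exact) method", with a two-sided 95% interval, for all 30 patients and then by treatment history.
- Sections 6.1 and 6.2 attach a criterion of 20% or greater to a positive scan. Section 6.2 says that a therapeutic trial will follow if it is met.

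No section says how the and/or is to be read, or how a lesion is graded when spleen uptake is not above liver uptake.

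**The concern.** One percentage is the main result and carries the 20% criterion. Three descriptions feed it: the SSTR-positive rule, the moderate-to-high grades, and the phrase in 6.4. They should pick out the same patients, and as written they do so only under conditions that the plan leaves unstated.

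The firmer problem lies inside 4.6.4. High binding refers only to spleen, whereas low binding and SSTR positivity refer to liver. Nothing stops a lesion from meeting both the low and the high description, and such a lesion would be positive for the endpoint and negative under the study's own positivity rule. The second problem is drafting: the sentence that generates the number uses and/or where the endpoint has a defined term. If either point has to be settled once scans have been read, the choice is made with the results in view.

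**Working it through.** **Planned intervals.** Section 6.2 gives 7.7% to 38.6% at 20% positive with N = 30, and 4.3% to 48.1% with n = 15. The Clopper-Pearson limits are: lower = the 0.025 quantile of Beta(x, n − x + 1); upper = the 0.975 quantile of Beta(x + 1, n − x).

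- x = 6, n = 30: 7.71% to 38.57%.
- x = 3, n = 15: 4.33% to 48.09%.

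Both reproduce. They depend only on x and n, so the definitions do not affect them.

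**Do the definitions agree?** Let T be lesion uptake, L adjacent liver and S spleen, with skeletal muscle below all three. From 4.6.4: low is T ≤ L; moderate is L < T < S; high is T ≥ S; SSTR-positive is T > L. From 5.1: the endpoint is moderate or high. The 6.4 phrase is either (T > L or T > S) or (T > L and T > S).

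| Order | Lesion | Grade in 4.6.4 | Endpoint 5.1 | SSTR-positive | 6.4 as or | 6.4 as and |
|---|---|---|---|---|---|---|
| S > L | T ≤ L | low | no | no | no | no |
| S > L | L < T < S | moderate | yes | yes | yes | no |
| S > L | T = S | high | yes | yes | yes | no |
| S > L | T > S | high | yes | yes | yes | yes |
| S = L | T < L | low | no | no | no | no |
| S = L | T = L = S | low and high | yes | no | no | no |
| S = L | T > L | high | yes | yes | yes | yes |
| S < L | T < S | low | no | no | no | no |
| S < L | T = S | low and high | yes | no | no | no |
| S < L | S < T ≤ L | low and high | yes | no | yes | no |
| S < L | T > L | high | yes | yes | yes | yes |

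Four things follow.

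1. With spleen above liver, the endpoint, the SSTR-positive rule and the inclusive or select the same lesions.
2. With spleen at or below liver, moderate is empty and low overlaps high. When the two organs are equal, the overlap is only the exact tie.
3. Every SSTR-positive lesion meets the endpoint in all three orders, so the overlap can only raise the endpoint count above the SSTR-positive count.
4. The and reading loses all moderate lesions and those equal to spleen when spleen is above liver, so it can only lower the count.

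**Size, with assumed counts** (the documents give none):

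- *Overlap.* Suppose 5 of 30 patients have a lesion above liver: 5/30 = 16.7% (exact 95% CI 5.6% to 34.7%). One further patient whose lesion is both low and high makes the endpoint count 6/30 = 20.0% (7.7% to 38.6%). The first misses the 20% criterion and the second meets it.
- *The and reading, which the documents do not support.* Suppose 8 of 30 are above liver and 3 of those are above spleen. Above liver gives 8/30 = 26.7% (12.3% to 45.9%); the and reading gives 3/30 = 10.0% (2.1% to 26.5%).

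**The case against.** The strongest reply is that the scale in 4.6.4 rises through muscle, liver and spleen. Moderate binding can exist only if spleen is above liver, so the authors plainly assumed that order. Under it, the natural inclusive reading of 6.4 is the endpoint of 5.1. This stands. A reader might infer that 6.4 analyses a different quantity from 5.1, and as a general statement the documents do not support that. Even with spleen below liver, the or reading departs from the 5.1 endpoint only for a lesion exactly tied with spleen. The conflict there is mainly between two rules within 4.6.4.

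A second reply is that the 20% criterion in 6.1 and 6.2 refers to a positive scan, for which 4.6.4 gives an explicit lesion rule, and that 6.2 uses positive binding and moderate-to-high binding for the same quantity. This also stands as evidence of intent. It does not settle the overlap: when spleen is at or below liver, those two terms stop meaning the same thing.

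A third reply is that this is a descriptive pilot without a formal test, and that the overlap may be rare. Both are fair limits on its weight. The percentage is nevertheless the primary result, and 6.2 ties a subsequent trial to it.

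**Conclusion.** The point holds as an inconsistency in the classification rules, together with an ambiguous sentence in the analysis plan. The overlap of low and high binding follows from the text alone whenever spleen uptake is at or below liver uptake. Its effect is one-directional, because it can add patients to the endpoint who are SSTR-negative under 4.6.4. Its size cannot be stated: the documents do not say how often that order occurs or how often a lesion falls in the gap. The move from 16.7% to 20.0% shows only that one such patient is enough when the count is next to the threshold.

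A reader might also infer that the result could swing from 26.7% to 10.0% according to how the and/or is read. That contrast uses assumed counts and needs the phrase to mean and alone. That would discard the moderate lesions that 5.1 and 6.2 expressly count and 4.6.4 calls positive. It illustrates what an unsupported reading would do and is not a likely outcome. The remaining fault is that the 6.4 sentence does not itself exclude it.

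The change should be made before images are read. It does not call the design or the planned precision into question.

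**What to change.** 1. In 1.1, 5.1 and 6.4, state one primary definition: a patient is positive if HCC activity is higher than adjacent uninvolved liver, that is, moderate or high binding. Delete the and/or spleen wording from the primary analysis sentence in 6.4 and from its counterpart in 1.1.
2. In 4.6.4, define high binding as higher than adjacent liver and equal to or greater than spleen. Low and high are then exclusive, and moderate plus high equals SSTR-positive whatever the order of spleen and liver. The authors should adopt this knowingly: where spleen is at or below liver, it removes from the endpoint lesions that the present wording of high would admit. It follows their own positivity rule.
3. Report the high-binding count separately with its own exact 95% interval, so that the comparison with spleen is kept as a descriptive result.

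The cost is a wording amendment to 1.1, 4.6.4, 5.1 and 6.4. No extra data, scans or patients are needed, and the intervals in 6.2 stay as they are.

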3.3 Inclusion Criteria

- Known diagnosis of hepatocellular carcinoma, either by imaging criteria or pathology on biopsy
- Standard of care liver MRI or CT demonstrating viable HCC based on arterial contrast enhancement measuring at least 1.5 cm in largest axial dimension

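### PET–liver MRI concordance is listed as a primary endpoint without restriction, but its 1-5 ratings, and on the most natural reading its analysis, cover PET-positive patients only

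*Combined protocol and SAP*

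**What the plan says.** **Endpoint and population.** Section 5.1 has two entries under Primary Endpoint. The second is concordance between "PET results and liver MRI results", with no population attached. Section 6.3 states that every patient with a "PET/MRI or PET/CT scan will be included in the analysis".

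**Image reading.** Under 4.6.4 every scan receives a first call: "Images will initially be interpreted as positive or negative for SSTR-positive HCC". A lesion is positive if its uptake exceeds that of adjacent uninvolved liver. The next step is limited. It begins "For patients with SSTR-positive HCC and positive" PET, and only there are intrahepatic and extrahepatic disease scored from 1 (negative) to 5 (definite), on MRI/CT alone and then on fused images. No section provides these scores for PET-negative patients.

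**Analysis.** Section 6.4 ties concordance to the same group: "PET results and liver MRI results for patients with SSTR-positive HCC and positive" PET. The sentence is a run-on that merges the analysis with the reading procedure. The binary cut-off follows: "assessed and rated on the same 1-5 scale. Scale 3-4" is what counts as positive. Cohen's kappa is then planned for a "nominal (e.g. scale 1-5) or binary outcome (positive or negative"), and that sentence names no population.

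**Eligibility.** Section 3.3 requires "Standard of care liver MRI or CT demonstrating viable HCC based on arterial contrast enhancement measuring at least 1.5 cm" in largest axial dimension.

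**The concern.** Concordance is a comparison of two results. If patients enter it because one result is positive, the PET-negative, MRI/CT-positive combination is removed by design, and PET-positive patients alone cannot show how often it occurs. A reader of 5.1 would expect a statement about all scanned patients, whereas the plan in 4.6.4 and 6.4 delivers one about a minority of them if positivity is near 20%.

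The selection can also make the PET margin constant, in which case kappa carries no information about agreement. The cut-off adds a separate problem: taken literally, the most confident positive score is not counted as positive.

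**Working it through.** **1. The plan's own figure.** Section 6.2 assumes 20% positive in 30 patients, that is 6/30. The Clopper-Pearson limits are the 2.5% quantile of Beta(6, 25) and the 97.5% quantile of Beta(7, 24), which give 7.71% and 38.57%. This reproduces the stated 7.7% to 38.6%. The plan gives no expected kappa or precision for concordance.

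**2. How many patients would have ratings.** The PET-positive count is Binomial(30, p); ranges are 2.5% and 97.5% quantiles.

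| p | Source | PET-positive | PET-negative (no 1-5 ratings) |
|---|---|---|---|
| 0.20 | Section 6.2 | 30 × 0.20 = 6 (2 to 11) | 24 (30 − 11 = 19 to 30 − 2 = 28) |
| 0.50 | Top of the tissue-based range in 1.2; carrying it over to PET is an assumption | 15 (10 to 20) | 15 (10 to 20) |

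**3. Binary kappa when PET is positive in every selected patient.** Kappa = (po − pe)/(1 − pe). With n selected patients, all PET-positive, and m of them MRI/CT-positive:

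- po = m/n
- pe = [n·m + 0·(n − m)]/n² = m/n

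So kappa is 0 for every m < n, and 0/0 when m = n. With 5 of 6 agreeing, po = pe = 0.833 and kappa is 0. With 14 of 15 agreeing, po = pe = 0.933 and kappa is again 0. With 6 of 6 or 15 of 15, it is undefined.

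**4. Forms that need not be degenerate (assumed data, six PET-positive patients).**

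- One fused score falls below 3: four patients positive on both, one positive on fused images only, one negative on both. Then po = 5/6 = 0.833, pe = (4·5 + 2·1)/36 = 0.611, and kappa = 0.222/0.389 = 0.57.
- Full 1-5 scale, with MRI/CT scores 3, 4, 4, 5, 5, 5 and fused scores 4, 4, 5, 5, 5, 5. Then po = 4/6 = 0.667, pe = (2·2 + 3·4)/36 = 0.444, and kappa = 0.40.

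**5. The cut-off.** Take the second set of scores in step 4. If only 3 and 4 are positive, MRI/CT is positive in three patients and fused images in two of those three. Then po = 5/6, pe = (3·2 + 3·4)/36 = 0.5 and kappa = 0.67. If 3 to 5 is positive, all six are positive on both and kappa is undefined. The 0.67 arises only because definite disease is counted as not positive.

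**6. Does opening the analysis to all 30 restore patient-level binary kappa for intrahepatic disease?** The number of MRI/CT-negative reads is not in the documents. Section 3.3 suggests few, so 28 to 30 positive reads are assumed. With 6 PET-positive:

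| MRI/CT-positive of 30 | pe | po, lowest to highest | Kappa, lowest to highest |
|---|---|---|---|
| 30 | (30·6 + 0·24)/900 = 0.20 | 0.20 | 0 |
| 29 | (29·6 + 1·24)/900 = 0.22 | 5/30 to 7/30 | −0.07 to 0.02 |
| 28 | (28·6 + 2·24)/900 = 0.24 | 4/30 to 8/30 | −0.14 to 0.04 |

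The lowest value puts every MRI/CT-negative patient among the PET-positives, and the highest puts every one among the PET-negatives. With 15 PET-positive, kappa is 0 at 30 positive reads and −0.07 to 0.07 at 29. Widening the population therefore does not by itself make this kappa informative.

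**The case against.** Four points can be made for the plan.

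- **The restriction may be deliberate.** It appears in the same terms in 4.6.4 and 6.4, and 5.1 is a one-line label. Adding the qualifier to 5.1 would also reconcile the wording. That is fair as to wording, but agreement would still be conditioned on the PET result.
- **The kappa sentence is unrestricted.** Every patient has an initial positive/negative PET call, so a binary comparison in all scanned patients is possible. The plan does not say it is intended, and the 1-5 comparison still could not be made in PET-negative patients.
- **A reader might infer that the planned kappa must be 0 or undefined.** The documents do not support that. The order of 6.4 suggests that the binary outcome is the dichotomised 1-5 score, and selecting on the initial PET call does not fix that score by definition. The 1-5 scale and extrahepatic disease are also free to vary. The degenerate result belongs to one conditional form. With 5 counted as positive, though, intrahepatic fused scores in PET-positive patients would probably be nearly constant.
- **A reader might also infer that 6.4 contradicts 6.3.** It does not: 6.3 defines an overall population, and analysing a subset of it is compatible. The mismatch is with the unrestricted endpoint in 5.1.

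The study is described as largely exploratory, with no hypothesis test, so no error rate is at stake.

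**Conclusion.** The concern holds as a mismatch between a listed primary endpoint and the data collected for it. The limit on the ratings is explicit in 4.6.4. The limit on the concordance analysis is the most natural reading of a garbled sentence in 6.4, not the only one. Followed that way, the analysis leaves out about 24 of 30 patients at 20% positivity (19 to 28), or about 15 (10 to 20) if 50% applied to PET.

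The 0-or-undefined kappa is exact algebra, but it requires PET to count as positive in every selected patient, with the patient as the unit and intrahepatic disease as the target. Every other form describes PET-positive patients only. The omission of score 5 is a separate defect on the literal text.

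Two limits apply. The 20% criterion rests on the first endpoint and is unaffected. The PET-positive restriction is also not the only reason kappa is uninformative here: eligibility makes MRI/CT nearly constant, an inference from 3.3 rather than a stated figure. This should be fixed, as a matter of definition and reporting.

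**What to change.** 1. In 4.6.4 and 6.4, delete the PET-positive restriction. Have the same readers score MRI/CT alone and then fused images on the 1-5 scale in all scanned patients. Keep results in PET-positive patients as a labelled subset.
2. In 6.4, define scores 3 to 5 as positive.
3. Beside any kappa, report the 2x2 counts and the percentage of MRI/CT-positive patients who are PET-positive, with an exact CI. If all 30 MRI/CT reads are positive and 6 patients are PET-positive, this is 6/30 with the 7.7% to 38.6% interval already given in 6.2.

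The cost is an amendment to the wording of two sections and extra reading time for PET-negative scans that will already have been acquired: about 24 at 20% positivity, about 15 at an assumed 50%, and 10 to 28 over the two binomial ranges. No further patients or scans are needed.

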6.2 Sample Size Justification

As this is a pilot feasibility study, no formal hypothesis will be testing, and thus no power analysis was performed. The primary objective is to determine the frequency of somatostatin receptor positivity in hepatocellular carcinoma using [⁶⁸Ga]DOTATATE-PET. In this study, patients with treatment-naïve HCC (n=15) and patients with previously treated HCC being referred for systemic chemotherapy and/or best supportive care (n=15) will be enrolled through the UAB Hepatobiliary Tumor Board in order to estimate the percentage of patients with moderate to high binding of [⁶⁸Ga]DOTATATE on PET examinations. Patients will undergo a single whole body [⁶⁸Ga]DOTATATE-PET/MRI or PET/CT to assess SSTR positivity of their HCCs. If a sufficient fraction (20% or greater) of HCC seen on conventional anatomic imaging demonstrate levels of somatostatin receptor expression to result in a positive DOTATATE PET scan, a subsequent therapeutic clinical trial with [¹⁷⁷Lu]DOTATATE will be carried out. With a total of 30 patients enrolled, the estimated percentage of positive binding of [⁶⁸Ga]DOTATATE will have two-sided 95% confidence intervals (CI) from $7.7\% \leq p \leq 38.6\%$ using the Clopper-Pearson (exact) method assuming at least 20% positive binding occurs. Although the confidence interval will be wide for each subgroup, e.g. treatment-naïve HCC or previously treated HCC with n=15 (95% CI $4.3\% \leq p \leq 48.1\%$), it will provide early evidence if the [⁶⁸Ga]DOTATATE binding will be affected by prior treatment and/or stage of disease.

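### The positive/negative cut in section 6.4 (scores 3-4) leaves out score 5, the definite end of the scale, so the binary PET versus liver MRI concordance is wrong as written

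*Combined protocol and SAP*

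**What the plan says.** Sections 4.6.4 and 6.4 describe the same two-step read. Section 4.6.4 gives the rated set: "For patients with SSTR-positive HCC and positive [⁶⁸Ga]DOTATATE PET, intrahepatic and extrahepatic disease will be assessed on MRI/CT alone first". Section 6.4 gives the scale: "with confidence in interpretation rated on a 1-5 scale (1 = negative, 5 definite". Scores 2, 3 and 4 have no label in either section.

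The fused images are then scored the same way, and the cut follows: "fused PET/CT or PET/MRI images will be assessed and rated on the same 1-5 scale. Scale 3-4" and, after a page break, "is defined as positive". The sentence is complete across the break, with no sign of lost text. Section 4.6.4 gives no cut.

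The cut is used in the next sentence of section 6.4: "The agreement (concordance) between nominal (e.g. scale 1-5) or binary outcome (positive or negative". That agreement is to be measured by Cohen's kappa. Section 5.1 lists the quantity as one of two bullets under Primary Endpoint: "Concordance between [⁶⁸Ga]DOTATATE PET results and liver MRI results".

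**The concern.** A positivity rule on an ordered confidence scale should not reverse as confidence rises. This one does: 1 and 2 are not positive, 3 and 4 are, and 5 is not. A two-class outcome has no third place for 5. An analyst who programs the sentence literally either puts 5 with 1 and 2 or treats it as unclassified.

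If 5 is negative, two errors follow, in opposite directions:

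- A patient scored 4 on MRI/CT and 5 on fused images counts as discordant, although both reads say disease.
- A patient scored 1 on MRI/CT and 5 on fused images counts as concordant, although the reads contradict each other.

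If 5 is unclassified, the most confident reads leave the analysis. In neither case can a reader of the result tell which way kappa has moved.

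The raw scores will exist and could be recoded. But the cut for a quantity listed as a primary endpoint would then be chosen with the ratings known.

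**Working it through.** **Inputs from the documents.** Scale 1-5 with 1 = negative and 5 = definite (4.6.4, 6.4); positive = 3-4 (6.4); only PET-positive patients rated (4.6.4, 6.4); n = 30 and 20% positive, the section 6.2 planning case: "assuming at least 20% positive binding occurs".

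**The plan's own figure.** The plan states no kappa and no sample size for concordance. The one related figure is the exact interval in section 6.2. Clopper-Pearson for 6/30 gives 7.71% to 38.57%, which reproduces the stated 7.7% to 38.6%.

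**How many patients would be rated.** 0.20 × 30 = 6. At the interval limits, 0.077 × 30 = 2.3 and 0.386 × 30 = 11.6, so about 2 to 12.

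**The rule applied to each score.**

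| Score | As written (3-4) | 3-5 | 4-5 |
|---|---|---|---|
| 1 | negative | negative | negative |
| 2 | negative | negative | negative |
| 3 | positive | positive | negative |
| 4 | positive | positive | positive |
| 5 | not positive | positive | positive |

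**Effect on kappa.** κ = (po − pe)/(1 − pe), where po is observed agreement and pe is the agreement expected from the margins. The score sets are assumed, with six pairs (MRI/CT, fused), one per patient, and 5 taken as negative under the written rule. Tables are [[both positive, MRI/CT only], [fused only, both negative]].

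- **(a)** (4,5)×3, (5,5)×2, (1,1)×1. As written: [[0,3],[0,3]], po = 3/6 = 0.500, pe = (3/6)(0/6) + (3/6)(6/6) = 0.500, κ = 0. With 3-5: [[5,0],[0,1]], po = 1, pe = (5/6)² + (1/6)² = 0.722, κ = 1.00. Positives on MRI/CT and fused are 3 and 0 as written, 5 and 5 with 3-5.
- **(b)** (1,5)×2, (4,4)×3, (1,1)×1. As written: [[3,0],[0,3]], κ = 1.00. With 3-5: [[3,0],[2,1]], po = 4/6 = 0.667, pe = (3/6)(5/6) + (3/6)(1/6) = 0.500, κ = 0.167/0.500 = 0.33.
- **(c)** (4,4)×3, (5,5)×2, (1,1)×1. κ = 1.00 under both rules, but positives per read are 3 as written and 5 with 3-5.
- **(d)** Score 5 never used: nothing changes.

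**If 5 is unclassified instead.** Dropping every pair that contains a 5 leaves 1 of 6 pairs in (a) and 4 of 6 in (b). In (b) the two contradictory pairs are the ones lost, and the remaining four still give κ = 1.00.

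**The replacement cut matters too.** For (3,4)×1, (4,5)×2, (5,5)×2, (1,1)×1:

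- As written: [[1,2],[0,3]], po = 0.667, pe = 0.500, κ = 0.33.
- 3-5: [[5,0],[0,1]], κ = 1.00.
- 4-5: [[4,0],[1,1]], po = 5/6 = 0.833, pe = (4/6)(5/6) + (2/6)(1/6) = 0.611, κ = 0.222/0.389 = 0.57.

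On the bands in section 6.4 these three results read as fair, very good and moderate.

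**A limit of kappa in this set.** If all pairs are positive on both reads, for example (4,5)×3 and (5,5)×3, the 3-5 rule gives [[6,0],[0,0]], pe = 1, and κ is undefined. The written rule gives κ = 0 on the same data.

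**The case against.** The case for treating this as minor has four parts.

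- **Role of the endpoint.** The stated objective is the frequency of positivity, and the step to a therapeutic trial rests on the 20% fraction. No decision depends on kappa, the analyses are described as largely exploratory, and the binary form is only one of two offered. This stands as a limit on the damage. But section 6.4 does not rank the two forms, so the binary result may be the one reported for a listed primary endpoint.
- **Wording.** The plan never says that 5 is negative; it leaves 5 unassigned. That is fair, and the kappas above apply only to the negative reading. The unassigned reading loses the most confident reads instead, so the rule fails either way.
- **Realism of the examples.** Entry requires viable HCC of at least 1.5 cm on MRI or CT, and only PET-positive patients are rated, so a score of 1 for intrahepatic disease is hard to picture. This stands for intrahepatic disease; for extrahepatic disease a score of 1 is quite possible. The unit of analysis is not stated, so one pair per patient is an assumption. Without its (1,1) pair, case (a) has undefined kappa under 3-5, although raw agreement still moves from 2/5 = 40% as written to 5/5 = 100%. The number rated could also be higher: the 20-50% tissue positivity cited in section 1.2 would give 6 to 15 of 30 if it carried over to PET.
- **Choice of cut.** The documents do not show that 3-5 was meant. That is correct, and it is why the sponsor must confirm the cut.

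**Conclusion.** The concern holds: the rule is wrong as written. It excludes the top category of its own scale from the positive class, and nothing elsewhere in the documents repairs it. This conclusion rests on the text alone.

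The size cannot be fixed from the documents, because it depends on how often 5 is used. In the assumed six-pair sets, replacing 3-4 by 3-5 moves kappa from 0 to 1.00, from 1.00 to 0.33, or not at all, so the direction cannot be predicted. Those figures assume one pair per patient, about six rated patients and 5 coded as negative.

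The harm is confined to the positive/negative version of the concordance. Kappa on the 1-5 scores and the percentage with moderate to high binding do not use this cut.

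**What to change.** Before images are read:

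1. Replace the cut in section 6.4 with: *Scores 3-5 are defined as positive; scores 1-2 are defined as negative.* This keeps the stated lower bound of 3. The sponsor should confirm that 4-5 was not intended.
2. Label scores 2, 3 and 4, and state the same cut in section 4.6.4.
3. Report the paired 2x2 counts beside the binary kappa, because kappa may be undefined when only PET-positive patients are rated.

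The cost is one line in section 6.4, repeated in 4.6.4, three score labels, one small table and one sponsor confirmation. No extra data, readers or patients are needed.
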